5.3.4 Multi-centre Studies

Because this study was not designed to detect centre effects with specific power, all centres will be grouped and analyses will be carried out as a whole. However, we will perform an exploratory analysis for centre effects with respect to each of the dependent variables. Qualitative and/or quantitative treatment-by-centre interactions will be investigated in this case. For the purpose of analysis, a small site will be defined as a site with < 4 ITT subjects in either treatment arm. Small sites will be ranked in descending order based on the total number of ITT subjects of the sites. The first small site will be pooled with the next small site, or with more sites if needed, until the pooled site/analysis centre has at least 4 ITT subjects in both the arms. The algorithm will continue down the list, and if the last few small sites are pooled but fail to be adequately large, they will be combined with the previously pooled smallest site/analysis centre.

5.4 Missing Data

Missing data will be imputed for some efficacy analyses described in the next sections (see section: efficacy analyses). Missing values will be imputed at all visits using the Multiple Imputation with Chained Equation (MICE) approach. Ten imputed data sets with all visit values filled in will be generated. The analysis will be performed on each of the 10 imputed datasets, which will produce estimates of treatment effect and the standard error of that estimate. Finally, the set of estimates and standard errors will be analysed by the *mice* R package to produce overall (pooled) estimates, confidence intervals, and P-values for the

treatment effect.

5.5 Interim Analyses and Data Monitoring (as applicable)

No interim analyses are planned for this study

5.6 Multiple Testing

There is no need to control for the overall type 1 error using a multiple testing procedure since there is only one single primary efficacy endpoint.

6 Summary of Study Data

[figure not shown]
All summary tables will be structured with columns for each treatment and overall in the order (Overall, Placebo, Empagliflozin) and will be annotated with the total population size relevant to that table, including any missing observations. All continuous variables will be summarized using the following descriptive statistics: n (non-missing sample size), mean, standard deviation. The frequency and percentages (based on the non-missing sample size) of observed levels will be reported for all categorical variables. Demographic and clinical characteristics to be summarized will include all baseline variables. P-values will be added to compare baseline characteristics between Placebo and Empagliflozin groups.

Summary tables will be provided overall and also, if adequate, stratified according to: variables used in stratifying the randomization (i.e. Sex, T2DM status and Site), variables used in the subgroup analysis, and by visit.

6.1 Subject Disposition

A graphic showing an overview of the recruitment rate overall and by treatment groups will be provided. Also, a flow diagram will be provided as shown below:

Flow Diagram

Tables showing the number of patients reaching v1 only, v1-v2, v1-v3 and v1-v4 will be

displayed according to the treatment groups. The same information will be provided about missing data on the primary endpoint.

The absolute change in nt-proBNP levels from randomization to week 26 denoted by 'change proBNP' and will be derived as follows:

change_proBNP = proBNP_w1 - proBNP_w26

where proBNP_w1 stands for the level of nt-proBNP at randomization (w1), and proBNP_w26 stands for the level of nt-proBNP at week 26.

The percentage change in nt-proBNP denoted as 'perc_change_proBNP' will be derived as follows:

perc_change_proBNP = (proBNP_w1 - proBNP_w26)/proBNP_w1 where proBNP_w1, and proBNP_w26 are defined as above.

6.2 Treatment Compliance

Treatment compliance will be assessed by remaining pill count. The pill count is checked at the monitoring visits.

7 Efficacy Analyses

Efficacy analyses performed using the intent-to-treat (ITT) population will be considered as primary, whereas efficacy analyses performed using the per-protocol (PP) population will be considered as supportive.

7.1 Primary Efficacy Analysis

The primary efficacy endpoint is the change in NT-proBNP from baseline to week 26. This primary endpoint will be analysed on the ITT population using a linear mixed effect model (LMEM) where the dependent variable is the NT-proBNP and the fixed effects are treatment, visit, treatment by visit interaction, the stratification factors Sex and T2DM and the level of NT-proBNP at baseline. The random effect component will include patients and unstructured covariance will be assumed for the within-subject errors. In case of non-convergence problems other covariance structures, such as compound symmetry, will be applied until the problem is resolved.

In this analysis, no missing data will be imputed. It will be handled by using the LMEM which assumes the data to be missing at random (MAR process). At week 26, estimates of mean values, the mean differences between the treatment groups and the associated 2-sided 95% confidence interval will be derived from the LMEM model through the use of estimated marginal means (or LS-means).

To claim superiority of Empagliflozin over Placebo, this primary efficacy analysis must show a statistically significant effect of treatment at an alpha level of 5% and two-sided test direction.

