#### 7. STATISTICAL ANALYSES

#### 7.1 Sample size and power considerations

Previous data showed that nt-proBNP levels decrease by about 50% within 6 months after acute myocardial infarction. To detect a relative 40% larger reduction in nt-proBNP levels in the Empagliflozin group as compared to the placebo group with a power of 80% and an alpha-level of 0.05%, and assuming a correlation for nt-proBNP levels of 0.85, a sample size of 216 subjects in each group is necessary. To account for a dropout rate of about 10% each group will consist of 238 patients.

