5.3.2 Covariates adjustment

All analyses, including the primary analysis, will be adjusted for the variables used when stratifying the randomization. These variables are Sex and T2DM status. We will not be able to adjust for the variable centre as this might introduce too many categories. Analysis will also be adjusted for baseline levels of the dependent variables.

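### The primary model gives baseline NT-proBNP one slope for all visits and does not limit the response to post-baseline rows: a minor, avoidable loss of precision at week 26

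*SAP*

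**What the plan says.** SAP 7.1 models NT-proBNP on the ITT population with a linear mixed model. Its fixed effects are treatment, visit, the interaction of the two, "the stratification factors Sex and T2DM and the level of NT-proBNP at baseline". The only interaction is treatment by visit. A patient random effect is included, and "unstructured covariance will be assumed for the within-subject errors". If the model does not converge, "other covariance structures, such as compound symmetry, will be applied until the problem is resolved". The treatment effect is read from the model at week 26 and tested "at an alpha level of 5% and two-sided test direction".

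SAP 5.3.2 repeats the baseline adjustment without qualification: "Analysis will also be adjusted for baseline levels of the dependent variables". Under Analyses of Secondary Endpoints, the continuous secondary endpoints follow the primary approach.

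Neither section says which visits form the response. In SAP 3.4 the baseline assessment is itself numbered as Visit 1, and SAP 6.1 treats it as the first in the series of NT-proBNP values.

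**The concern.** In a repeated-measures model the best baseline slope at a visit is the baseline correlation times the SD at that visit, divided by the baseline SD. A main effect alone forces these slopes to be equal across visits. If they are not equal, the shared slope misses the week-26 slope, and variance that baseline could have explained stays in the one contrast on which the superiority claim rests.

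Protocol Appendix A puts the SD at 772.98 at baseline and 289.60 at six months, so a spread that is still falling between weeks 6 and 26 is plausible.

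The undefined response is a second, related gap. If the baseline row is also a response, baseline is regressed on itself. That row has a slope of exactly 1 and pulls the shared slope upwards.

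What is at stake is the width of the week-26 confidence interval.

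**Working it through.** **Inputs from the documents.** Protocol 7.1 and Appendix A give means of 653.66 (baseline) and 282.66 (six months), SDs s0 = 772.98 and s26 = 289.60, correlation r = 0.85, and 216 per group after a 40% relative reduction ("To detect a relative 40% larger reduction in nt-proBNP levels in the Empagliflozin group"). No SDs or correlations are given for weeks 6 and 12, so those are assumptions below.

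**1. The plan's own sample size.**
- Difference = 0.4 × (653.66 − 282.66) = 148.4.
- Variance ratio = (289.60/772.98)² = 0.1404.
- Change-score SD = 772.98 × √(1 + 0.1404 − 2 × 0.85 × √0.1404) = 548.5.
- With two-sided 5% alpha and 80% power, n = 214.4, so 215 per group against 216 stated. Adding 10% gives 216 × 1.1 = 238.
- The alpha of 0.05% printed in the sample-size text would need 511 per group, so 5% was used.
- The implied standard error is 548.5 × √(2/216) = 52.8.

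**2. Week 26 with its own slope.**
- Slope = 0.85 × 289.60/772.98 = 0.318.
- Residual variance = 289.60² × (1 − 0.85²) = 23,273, so the residual SD is 152.6.
- Standard error = 152.6 × √(2/216) = 14.7.

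**3. Week 26 with a shared slope b (complete data).** The estimate is the week-26 difference minus b times the baseline difference. Its variance relative to step 2 is

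1 + (b − 0.318)² × 772.98²/23,273 = 1 + 25.67 × gap².

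A gap of 0.05 costs 6% and a gap of 0.10 costs 26%. Under compound symmetry, b is the plain mean of the visit slopes. Under unstructured covariance, b is their mean weighted by the inverse residual covariance matrix.

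**4. Worked cases (assumed SDs at weeks 6 and 12; r at week 26 is 0.85).**

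| Case | Visit slopes (weeks 6, 12, 26) | b | Variance |
|---|---|---|---|
| 290 and 290, all r = 0.85, compound symmetry | 0.319, 0.319, 0.318 | 0.319 | +0% |
| 350 and 310, all r = 0.85, compound symmetry | 0.385, 0.341, 0.318 | 0.348 | +2% |
| 450 and 350, r = 0.90 at weeks 6 and 12, compound symmetry | 0.524, 0.408, 0.318 | 0.417 | +25% |
| 450 and 350, all r = 0.85, follow-up correlations 0.80, unstructured | 0.495, 0.385, 0.318 | 0.362 | +5% |

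In the last case the standard error is 15.0 against 14.7. A simulation of 4,000 trials with the same assumed SDs and a shared slope of 0.363 gave 14.95 against 14.64.

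**5. Ranges.**
- SDs 290–450 (week 6) and 290–350 (week 12), baseline correlations 0.85–0.90, residual correlations 0.5–0.7: variance +0–11% under unstructured covariance (typically 1–3%) and +0–25% under compound symmetry (median about 8%).
- A wider set of 1,457 assumed combinations (week-6 SD 300–600, week-12 SD 290–500, baseline correlations 0.5–0.95): standard-error ratio 1.01 at the median, 1.08 at the 90th percentile and 1.41 at most under unstructured covariance. Under compound symmetry the figures are 1.05, 1.20 and 1.53.
- Log scale, which SAP 5.3.1 permits (log SDs 1.35 and 1.11 from the quartiles): up to about 7% in variance in the cases tried.

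**6. Baseline row also a response, under compound symmetry.** The shared slope becomes (sum of the three visit slopes + 1)/4.
- 350 and 310: (1.044 + 1)/4 = 0.511, gap 0.193, variance ratio 1.95.
- 450 and 350 with r = 0.90 at weeks 6 and 12: (1.250 + 1)/4 = 0.562, gap 0.244, variance ratio 2.53.
- SDs already settled at 290: gap 0.171, variance ratio 1.75.

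These ratios are true sampling variances. The standard error that a compound-symmetry fit prints is pooled over visits and need not equal them.

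**The case against.** A reader might infer from the SD falling from 773 to 290 that the shared slope is too steep at week 26. The documents do not support this. That fall is from baseline to six months, and loss arises only if slopes differ among weeks 6, 12 and 26. If spread and correlation have settled by week 6, the loss is zero. A fall in level alone is absorbed by the visit effect. Under unstructured covariance the shared slope leans towards the visits with small residual variance and can even fall below the week-26 slope. This objection stands.

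A reader might also infer that power is at risk. It is not. The sample size was set on the unadjusted change score with a standard error of 52.8. Power for a difference of 148.4 stays above 99.9% under unstructured covariance in every combination tried. Even a 2.53-fold variance gives 14.7 × √2.53 = 23.4, less than half of 52.8.

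Nor is the correction of a chance baseline imbalance with the wrong slope a second harm. It is the same variance term. Randomisation keeps the complete-data contrast unbiased.

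Secondary Efficacy analysis III is a week-26 regression with its own baseline slope and would expose a material difference. SAP 7.2, however, rests the superiority conclusion on the primary analysis alone, so it is only a partial safeguard.

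The larger figures need the compound-symmetry fallback, which applies only after non-convergence. That branch is not remote. A patient random effect is not separately identifiable beside a fully unstructured error covariance. A baseline response row would also have zero residual at slope 1, which makes that covariance singular.

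**Conclusion.** The omission is real and its effect is minor. SAP 7.1 has no baseline-by-visit term and no definition of the response rows. Asymptotically, a visit-specific slope cannot be less precise at week 26 than a shared one.

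Under the specified covariance the loss is probably a few percent of variance, and possibly none. It reaches up to about 25% under the fallback. The roughly 2- to 2.5-fold figure needs both a baseline response row and the fallback. All these sizes rest on assumed week-6 and week-12 SDs and correlations and on complete data.

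Week 12 has no biobank sample in the visit schedule, so it may contribute only local values, which SAP 8.3 accepts when a central measurement is not possible. With weeks 6 and 26 alone, the standard-error ratio was 1.00–1.09 under unstructured covariance.

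This is a point about efficiency and specification. It does not show bias or an underpowered trial. The documents give no figures on how slopes behave for the secondary endpoints.

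**What to change.** In SAP 7.1, add a baseline-by-visit interaction to the fixed effects. State that the response vector contains only the post-baseline visits (weeks 6, 12 and 26), with baseline NT-proBNP as a covariate only. Use the same form for the continuous secondary endpoints that follow the primary approach, at the post-baseline visits where each is measured. There it is a matter of consistency, not of a demonstrated loss.

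The cost is two sentences and two further parameters in the primary model, against 432 evaluable patients planned (2 × 216). No new data are needed and the sample size does not change. Stating the response rows is the more valuable half, because it removes the only branch with a large loss.

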## 5.5.6 Blood sample collection and plasma extraction for biobanking

Blood will be collected via venous puncture into 16ml serum, 6ml EDTA and 4ml sodium citrate vacutainers and centrifuged within 30 min of collection. Plasma should be transferred into Eppendorf tubes and stored at -80°C locally. In regular intervals these samples will be shipped on dry ice to the Biobank of the Medical University of Graz, where they will be stored at -80°C for future biomarker analyses. NT-proBNP and blood ketone bodies will be measured in batches from these stored biomarker samples.

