3.4 Study Assessments

Data are collected according to the following schedule:

	Visit 1 (V1) Screening / Baseline	Visit 2 (V2) (week 6 ± 2)	Visit 3 (V3) (week 12 ± 2)	Visit 4 (V4) (Week 26 ± 2)	Visit 5 (V5) (4 weeks ±1w after V4)
Informed Consent	X				
Inclusion/exclusion criteria	x				
Randomisation	x				
Demography, medical history	x			6.	
Concomitant medication	X	x	X	×	
Vital signs	x	x	x	x	
Height	х		0	OX	000
Weight	x	x	x	x	6
Physical examination	x	x	.00	x	
ECG	X			7	
Cardiac ultrasound	x	x		x	
Biobank sampling	x	x		×	
nt-proBNP (local)	x	x	x	x	
Blood sampling	X	x	x	x	
Liver function parameters (AST, ALT, GGT)	x	×	X	x	
Renal function parameters (creatinine, eGFR)	X	x	x	X	
Adverse Events	1 10	X	X	X	X
Dispense medication	X				
Drug accountability				X	
Safety assessment before discharge	×		V.		

4 Sample Size

Previous data showed that NT-proBNP levels decrease by about 50% within 6 months after acute myocardial infarction. To detect a relative 40% larger reduction in NT-proBNP levels

in the Empagliflozin group as compared to the placebo group with a power of 80% and an alpha-level of 0.05%, and assuming a correlation for NT-proBNP levels of 0.85, a sample size of 216 subjects in each group is necessary. To account for a dropout rate of about 10% each group will consist of 238 patients. A detailed document regarding power and sample size calculation is annexed to this SAP.

5 General Analysis Considerations

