7.2 Secondary Efficacy Analyses

To support the interpretation of the primary efficacy analysis, some robustness and/or sensitivity analyses will be performed on the primary efficacy endpoint. However, the conclusion of superiority for comparison of the primary endpoint between the two treatment groups is purely based on results of the primary efficacy analysis.

Secondary efficacy analyses will be performed to assess robustness of the results against missing data, analysis population, and the statistical model used.

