7.2.2 Secondary Efficacy analysis II

To assess the sensitivity of the above primary efficacy analysis to the analysis population, we will conduct the same primary efficacy analysis as above but by using the Per protocol

Statistical Analysis Plan EMMY trial

population instead of the ITT.

Secondary Efficacy analysis III

In this analysis, we use the absolute change in NT-proBNP from baseline to week 26 as the

primary endpoint. This endpoint will be analyzed on the ITT population, with no imputation

of missing values, and by using a multiple linear regression model where the dependent

variable is the absolute change in NT-proBNP and the independent variables are treatment,

Sex, T2DM and baseline level of NT-proBNP.

Secondary Efficacy analysis IV 7.2.4

In this analysis, we use the percent change in NT-proBNP from baseline to week 26 as the

primary endpoint. This endpoint will be analyzed on the ITT population, with no imputation

of missing values, and by using a multiple linear regression model where the dependent

variable is the percent change in NT-proBNP and the independent variables are treatment, Sex,

T2DM and baseline level of NT-proBNP.

Analyses of Secondary Endpoints

The change from randomization to week 26 of all continuous secondary endpoints will be

analysed in the same way as the primary efficacy endpoint as follows:

Analysis population: ITT

Missing data: no imputation to be performed. Missing data will be implicitly handled by using

the LMEM which assumes the data to be missing at random (MAR process).

Statistical model: LMEM with unstructured covariance matrix. At week 26, estimates of mean

values, the mean differences between the treatment groups and the associated 2-sided 95%

confidence interval will be derived from the LMEM model through the use of Least square

means (LS-means).

Safety Analyses

The safety section of the analysis will contain a descriptive listing of the following tables:

All-Cause Mortality: A table of all cases of deaths due to any cause, with number and frequency

of such events in each arm/group of the clinical study.

Serious Adverse Events: A table of all anticipated and unanticipated serious adverse events, grouped by organ system, with number and frequency of such events in each arm/group of the clinical study.

This table will also include the reporting of cases of diabetic ketoacidosis.

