8.3 Clinical Laboratory Evaluations

Summary statistics on laboratory measurements will be tabulated. For baseline values, differences in normal ranges between sites will be provided.

The primary outcome, NTproBNP, is assessed at the central lab. If measurement in the central lab are not possible (e.g. missing biomarker sample), NTproBNP measurement from the local lab will be accepted for the analysis.

9 Reporting Conventions

P-values ≥0.001 will be reported to 2 significant figures; p-values less than 0.001 will be reported as "<0.001". The mean, standard deviation, and any other statistics other than quantiles, will be reported to one decimal place greater than the original data. Quantiles, such as median, or minimum and maximum will use the same number of decimal places as the original data.

EMMY trial

Statistical Analysis Plan

EMMY trial

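### SAP 7.1 pairs a patient random effect with an unstructured covariance, one parameter too many, and its unordered fallback names only a structure that forces equal variances across visits

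*SAP*

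**What the plan says.** SAP 7.1 analyses NT-proBNP with a linear mixed model. The fixed effects are treatment, visit, their interaction, sex, T2DM and baseline NT-proBNP. On the covariance it says: "The random effect component will include patients and unstructured covariance will be assumed for the within-subject errors". If the fit fails: "In case of non-convergence problems other covariance structures, such as compound symmetry, will be applied until the problem is resolved". It does not say that the patient effect is dropped at that point, gives no order of structures, and does not list the visits that enter as responses.

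The SAP paragraph headed Analyses of Secondary Endpoints says that continuous secondary endpoints are "analysed in the same way as the primary efficacy endpoint as follows", and then describes the model without a random effect: "Statistical model: LMEM with unstructured covariance matrix".

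SAP 7.2 states that the superiority conclusion "is purely based on results of the primary efficacy analysis".

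On the measurements, SAP 8.3 says: "The primary outcome, NTproBNP, is assessed at the central lab", with the local laboratory value as substitute. Protocol 5.5.6 adds: "NT-proBNP and blood ketone bodies will be measured in batches from these stored biomarker samples". In the SAP 3.4 schedule the row "Biobank sampling" is marked at baseline, week 6 and week 26 but not at week 12. Local NT-proBNP is marked at all four visits.

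**The concern.** The sentence on covariance describes two models at once. A random patient intercept and an unstructured within-patient covariance are alternative ways to model correlation between visits. Used together, they cannot be separated by the data. The secondary-endpoint paragraph suggests that an ordinary repeated-measures model with one unstructured matrix was meant, but the primary analysis does not say so.

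The redundancy alone would be a matter of tidiness. It matters because of the sentence that follows it. If the software reports a failed fit, the analyst may try other structures until one works, and the only one named assumes the same variance at every visit. The covariance behind the single confirmatory p-value would then be settled after a fit to trial data has failed. If it imposes equal variances that do not hold, the week-26 standard error is wrong.

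**Working it through.** **1. Redundancy of the stated model.** Let V be the within-patient covariance over K response visits, J the matrix of ones, τ the patient variance and R the residual covariance, so V = τJ + R. With R unstructured, (τ, R) and (τ + c, R − cJ) give the same V for any c that keeps both admissible. An unstructured R has K(K+1)/2 parameters, and the patient effect adds one that V cannot use.

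| Response visits | Distinct elements of V | Parameters with patient effect | Rank |
|---|---|---|---|
| 2 | 3 | 4 | 3 |
| 3 | 6 | 7 | 6 |
| 4 | 10 | 11 | 10 |

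Removing the patient effect restores full rank.

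**2. Redundancy of the named fallback.** Compound symmetry is V = aI + bJ. With a patient effect it becomes aI + (b + τ)J: three parameters, rank 2, whatever the number of visits.

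**3. Effect on the week-26 result when the fit converges.** None. The contrast and its standard error depend on V only. At four different splits of the same V, the standard error was 14.68 each time.

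**4. Can the redundancy trigger the fallback?** The simulated trials had 476 patients, 10% missing completely at random at week 26, an assumed visit correlation of 0.7, and SDs at weeks 6, 12 and 26 of 1.22, 1.1 and 1.
- Singular REML Hessian: 100 of 100 trials for patient effect plus unstructured, and 100 of 100 for patient effect plus compound symmetry. Without the patient effect it was 0 of 100 for each structure.
- Optimiser convergence: two standard optimisers converged in 60 of 60 trials in the same setting, for both over-parameterised models.

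So the Hessian is singular, but whether that counts as non-convergence depends on the software. SAP 7.1 does not name the fitting routine.

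**5. Compound symmetry without the patient effect.** With complete data, the ratio of the reported to the true week-26 standard error is

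k = √(mean visit variance / week-26 variance), with true alpha = 2(1 − Φ(1.96k)).

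The variances are those left after baseline adjustment. Week-6 and week-12 values are not in the documents, so the SD ratios to week 26 below are assumed.

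| Week 6 / week 12 | k | True alpha |
|---|---|---|
| 1.22 / 1.1 | √((1.4884 + 1.21 + 1)/3) = 1.110 | 3.0% |
| 1 / 1 | 1.000 | 5.0% |
| 0.9 / 0.95 | √((0.81 + 0.9025 + 1)/3) = 0.951 | 6.2% |
| 0.8 / 0.9 | √((0.64 + 0.81 + 1)/3) = 0.904 | 7.7% |
| 1.22, weeks 6 and 26 only | √((1.4884 + 1)/2) = 1.115 | 2.9% |
| 0.8, weeks 6 and 26 only | √((0.64 + 1)/2) = 0.906 | 7.6% |

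Simulation with 10,000 null trials per scenario (Monte Carlo error about 0.2 points) gave 3.4% for 1.22/1.1, 8.1% for 0.8/0.9 and 5.3% for equal SDs. With robust standard errors the same three scenarios gave 5.5%, 5.1% and 5.5%.

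**6. Power.** The plan gives no figure for the covariance itself; its sample size is the nearest.
- Inputs from Protocol Appendix A: SDs 772.98 and 289.60, correlation 0.85, Δ = 0.4 × (653.66 − 282.66) = 148.4.
- SD of change: 772.98 × √(1 + 0.1404 − 2 × 0.85 × 0.3747) = 548.5.
- n = 2 × (1.96 + 0.8416)² × 548.5² / 148.4², which rounds up to 215 per group against the stated 216. The figure is reproduced.
- Under the baseline-adjusted model, the week-26 residual SD is 289.60 × √(1 − 0.85²) = 152.6, the standard error is 152.6 × √(2/216) = 14.68, and z = 148.4/14.68 = 10.1.
- With a reported standard error 27% too large, z is still 148.4/(14.68 × 1.27) = 8.0. Power is not at issue on the plan's own figures.

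**The case against.** The strongest reply is that nothing here changes the planned result. The redundant parameter leaves the week-26 contrast and standard error as they are. The secondary-endpoint paragraph shows the intended model, and that model fits without difficulty. A singular Hessian is not the same as non-convergence, and ordinary optimisers did converge. The SAP names compound symmetry only as an example, and a patient intercept with independent errors already is compound symmetry, so the fallback can be read sensibly. The test-size figures rest on assumed SDs, and a log transformation, which SAP 5.3.1 allows, could bring the visit variances closer together. Secondary analysis III regresses the week-26 change on treatment, sex, T2DM and baseline, which needs no between-visit covariance and would expose a distorted standard error.

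Most of this stands, and it limits the point. A reader might infer that the primary model cannot be fitted, that the fallback will be used, or that type I error is inflated. The documents support none of these. Appendix A's fall in SD from 772.98 to 289.60 concerns raw values at baseline and month 6. It makes equal variances doubtful on the raw scale but does not settle the baseline-adjusted variances at weeks 6, 12 and 26. Under the schedule, a week-12 NT-proBNP value would come from the local laboratory. That is a further reason not to assume equal variances, but it is not evidence of a difference.

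What remains is that the primary analysis and the paragraph said to mirror it describe different models, and that the fallback is open-ended. Secondary analysis III cannot repair this, because SAP 7.2 excludes it from the superiority decision.

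**Conclusion.** The point holds as a specification fault, minor to should-fix. As written, the primary model has one covariance parameter too many, and so does its only named fallback if the patient effect is kept. That is algebra and needs no assumption. The redundancy does not bias the week-26 estimate or its standard error in a converged fit.

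Harm requires three things together: the software treats the fit as failed, an equal-variance structure replaces it without robust standard errors, and the average baseline-adjusted variance over the visits differs from that at week 26. How often the first would occur cannot be known from the documents. Nor can the size or direction of the third. The range of about 3.0% to 7.7% for true alpha is an illustration under assumed SD ratios, not an estimate for this trial. No loss of power is claimed.

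**What to change.** In SAP 7.1:

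1. Delete the patient random effect. Specify one unstructured covariance over the post-baseline visits, with baseline NT-proBNP as covariate. This matches the secondary-endpoint paragraph.
2. Name the response visits, and say whether week 12 is included given that it has no biobank sample.
3. Replace the open fallback with a pre-specified order of structures that keep a separate variance at each visit. With three visits, one option is heterogeneous Toeplitz (3 variances, 2 correlations) and then heterogeneous compound symmetry (3 variances, 1 correlation). The exact order is the sponsor's choice.
4. If only weeks 6 and 26 are responses, both of these structures have 3 parameters and equal the unstructured model. State then that no simpler structure will be used.
5. Robust standard errors may be added whenever a fallback is used. The SAP should note that they correct the standard error but not any bias from a wrong working covariance when data are missing at random. The simulations above used data missing completely at random and do not test that case.

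The cost is SAP wording only, with no change to data collection or sample size.
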